5.4 Establishing and working within the Clinical Interpretation Partnership

The GeCIP has been organised into a series of disease-specific domains by an open call, in which UK researchers, trainees and the NHS self-organised and created proposed GeCIP domains. Key selection criteria were published in the GeCIP guidance document accompanying the call. Successful GeCIP proposals clearly articulate the value they will add to the clinical interpretation of the Genomics England dataset.

Researchers, NHS clinicians/healthcare professionals and trainees will work as part of **disease-specific** or **function specific domains** (depending on their area of expertise), contributing patients, phenotypes, knowledge, expertise, and undertaking research to add value. This work will be continuous, as the dataset is updated with patient outcomes and detailed clinical, phenotypic and laboratory data, which is collected during routine NHS care. Some clinicians will work in several domains if they have a broader clinical or laboratory remit.

[figure not shown]
The list of clinical domains described below is representative of the diseases we are now working on in the Genomics England pilots. It is subject to change at the discretion of Genomics England. In our **call for GeCIP domain proposals**, we encouraged the applicants to self-organise and make their own domain proposals. This may include domains not mentioned below. They will also be encouraged to propose a UK Lead and we will work with applicants to optimise the GeCIP domain as needed.

Diseas	Functional/Cross-cutting		
Cancers	Rare inherited diseases	domains	
Breast	Hearing and Sight	Analytical	
Lung	Cardiovascular disease	Ethics and Social Science	
Ovarian	Respiratory		
Colorectal	Endocrine and metabolism		
Prostate	Gastroenterology		
CLL/leukaemia	Immunological diseases		
	Neurological and degenerative disease		
	Musculoskeletal		
	Skin		
	Renal		
	Haematology		
	Paediatric		
	Inherited Cancers		
	Severe response to infection		
	Rheumatology	Feedback and Validation	

Table 1 - GeCIP domains.

The GeCIP domains can be led and proposed by researchers, NHS clinicians/healthcare professionals and those training anywhere in the UK. They are not confined to England.

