DNA purity	Should be measured.	A260/A280 ratio should be measured.
DNA buffer	1X TE pH8.0 / or as per manufacturers system**	

* We are working in a collaborative manner with Illumina to reduce the quality and quantity of DNA required for successful whole genome sequencing over the course of the project. Stated values are current guidance from Illumina as being required for reliable successful sequencing.

** Where proprietary buffers are included in the automated system these need to have been proven to be compatible with Illumina NGS technology

DNA extracted from blood and tumour must be sent together to the Biorepository, following confirmation that clinical data is available that meets Genomics England requirements as laid out in Genomics England SOPs.

For the main programme, it is expected that Genomics England and NHS England* will work in partnership to identify and implement changes to the molecular pathology pathways within accredited centres to enhance sample quality, in order to optimise the Genomics England pipeline. Such changes will be based on learning derived from phase 2 of the programme and relate specifically to tumour DNA samples from FFPE or fresh frozen preparations. As a result, it should be noted that some of the requirements may change over the life of the programme.

All DNA samples should be accompanied by an electronic and printed sample request form provided by Genomics England, which provides data on the patient and sample itself. It is to be completed at the point the sample is taken and prepared. Genomics England will work with the GMCs to finalise the following dataset and collection tool:

- DNA source germline/tumour, primary/metastasis.
- Standard Operating Procedure version(s) used for collection, extraction, QC and logistics.
- Tumour type (if cancer).
- Tumour cellularity percentage (if cancer).
- DNA concentration (nanogrammes/microliter).
- DNA volume (microliters).
- DNA QC metrics (to be finalised with sequencer).
- Genomics England identifier for data subject (site ID, local patient ID (NHS Number), sample ID).
- Gender and ethnicity.
- Date of birth.
- Pedigree structure and affectation status (rare disease).
- Version of Consent and Patient Information Sheet used.
- Syndrome or disease name.
- Named site contact and email (to verify receipt of samples by collection hubs, for queries etc.)

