8.4.5 DNA delivery to sequencer (logistics)

Paired tumour and blood DNA samples extracted in accredited Genomic Medicine Centres or in the Genomics England Central Biorepository. All samples and DNA should be provided to the Genomics England Central Biorepository as soon as possible using a specialist courier. The Biorepository and sequencer will be automatically notified of sample departure via the electronic sample request form.

Genomics England will provide a template and reporting timelines for this work.

Genomics England has committed to a sample schedule with the sequencing companies, and so sample logistics should follow the agreed schedule in order to optimise utilisation of the reserved capacity in the sequencing centre.

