Appendix 3 Biological samples standard operating procedures

Sample collection

- All samples should be taken specifically for this project, rather than using historic stored samples, except for rare occasions when agreed otherwise with Genomics England.
- Cancer patients should have their blood sample taken prior to biopsy or resection, and within an appropriate period of time to prevent changes due to treatment or blood transfusion.
- Patients with haematological cancers should have a peripheral blood sample taken along with a saliva sample.

All samples must be collected according to the following specification, using the Institution's Approved Standing Operating Procedures and performed by staff with appropriate training, and who receive regular competency checking in these procedures. Institutional safety guidelines for handling of human biological materials and hazardous chemical should also be followed.

Peripheral blood samples are collected for:

- DNA for whole genome sequencing (and storing for potential future epigenetic or other analysis).
- Stabilised blood for future RNA extraction.
- Serum and plasma for future proteomic and metabolomics studies.
- Cell free plasma for future analysis of circulating tumour DNA.

Two samples of blood are taken for DNA extraction, one to be stored at the Genomic Medicine Centre for local testing and validation, and one to be entered into the project and sent to the Biorepository along with the other samples using the centrally procured coordinated transport system.

Sample volumes

Cancer

	DNA (EDTA - purple)	Plasma (PST - green)	Serum (SST - gold)	RNA (Paxgene)	Saliva (Oragene)	
Adult (14yrs+)	4.5ml x 2 10ml x 1	10ml	10ml	5ml	-	
<14yrs	Specific guidance will be given for childhood cancers, please contact Genomics England before enrolling any adolescents or children for other cancer types					
CLL patients	As above	As above	As above	As above	2ml - Follow kit instructions	

Rare and Infectious Diseases

	DNA (EDTA - purple)	Plasma (PST - green)	Serum (SST - gold)	RNA (Paxgene)	Saliva (Oragene)
Adult (14yrs+)	4.5ml x 2	10ml	10ml	5ml	-
3-14 years	3ml x 2	3ml	3ml	2.5ml	-
0-3 years*	1-3ml	1 ml	1 ml	1ml	-

*In neonates and acutely ill children, clinical discretion should be applied to the volume of blood able to be extracted without risk of adverse events. Where only small volumes of blood are obtained, workflows should be altered to allow 'rescue' of plasma prior to automated DNA extraction.

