Prioritisation of samples

All efforts should be made to collect all indicated samples at the same time. If it is not possible to collect all samples, then the priority is to collect blood only for DNA extraction, followed by plasma, RNA (Paxgene) and then serum. If handling small blood samples, then 'rescue' of plasma prior to automated DNA extraction should be performed whenever possible.

Sample labelling

A unique identifier will be produced at the time of consent that should be used, along with NHS number, as the main identifiers within the clinical sites. A minimal sample collection form will be provided for completion of details at the time of collection. The majority of information will be electronically recorded in a tool provided by Genomics England. This will be done by interfacing with existing systems for ease of data transfer. The best methods for identification and labelling are currently being assessed by Genomics England and detailed information on what will be required will be provided at a later date in further guidance.

Sample transport to Genomic Medicine Centres

All samples must be placed in approved standard specimen bags with a collection form to be supplied and transported to the Genomic Medicine Centre processing laboratory(ies) for receipt within 24 hours of sample collection. RNA stabilised blood, and samples for plasma and serum for 'omics' studies, will degrade if they are not processed as soon as possible. Therefore, optimisation of transport logistics to the processing laboratory(ies) within a GMC from all sites of collection should be a priority.

Sample processing

Logging samples

All samples should be entered onto a LIMS and processed as soon as they reach the laboratory. All LIMS system must be able to:

- Create unique barcodes/identifiers based on guidance from Genomics England.
- For each patient codes need to be created for DNA, RNA, serum and plasma samples.
- Track samples at all stages from collection, through processing to dispatch.
- Comply with Information Governance Legislation.
- Export information to provide required data to Genomics England/NHS England.

Information will be provided in further guidance on appropriate tubes and identification to allow ease of handling and tracking when sent on to the Central Biorepository.

Sample processing (see flow diagram below for overview)

- DNA extraction.

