- RNA stabilised samples should be aliquoted, and then immediately frozen and stored at -80°C until transported to the Biorepository.
- Serum and plasma samples for proteomics and metabolomics should be separated (centrifugation at 1300-2000 G for 10 minutes) immediately frozen and stored at -80°C until transported to the Biorepository.
- Samples for circulating tumour DNA should be centrifuged at 1300-2000 G for 10 minutes at 4°C. The plasma supernatant should then be immediately transferred in 1ml aliquots to 2ml microtubes and centrifuged on a bench top centrifuge at 14,000rpm for 10 minutes. The plasma supernatant should

then be transferred to new tubes, immediately frozen, and stored at -80°C until transported to the Biorepository. The buffy coat should also be collected in a separate microtube and frozen at -80°C until transported to the Biorepository.

• Samples should be aliquoted into a barcoded Universal tube, or other tube as specified in future guidance.

Sample transport to Central Biorepository

- DNA should be transported at room temperature to the Central Biorepository by the agreed transport system.
- All plasma, serum and RNA stabilised blood aliquots should be transported in batches on dry ice at the appropriate temperature, stabilising the packaging by the agreed transport system, at intervals to be advised in further guidance.

Tumour sample collection and processing

Whole genome sequencing success rates from FFPE tumours to date are relatively low, but variable, with relatively limited experience in a number of centres. Evidence and clear best practice are lacking in a number of areas. We will work with centres, along with Illumina, to improve success rates through optimising procesures. It is important centres collaborate with this and follow additonal guidance and protocols produced, as best practice methods are agreed.

When a tumour is received in the laboratory, the following are essential for entry into the project:

- Tumours should have been biopsied or resected prior to treatment, apart from where normal clinical practice is to treat prior to resection or if the sample is from a recurrence (where the original tumour has previously been sequenced).
- A germline blood sample should have been collected prior to resection or biopsy.
- Samples should be placed in formalin for no more than 24 hours before processing to avoid fragmentation and transferred to the laboratory as soon as possible.

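### Appendix 3 asks for saliva in all haematological cancers, but its volume table schedules it only for CLL, and no section names saliva as the matched normal.

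*Protocol*

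**What the plan says.** Under Sample collection, Appendix 3 sets a rule without limit by diagnosis: "Patients with haematological cancers should have a peripheral blood sample taken along with a saliva sample". The next paragraph makes what follows binding: "All samples must be collected according to the following specification". In the cancer volume table under it, the general row for patients aged 14 and over has a dash for saliva. Only the CLL row has an entry, "2ml - Follow kit instructions", and that row takes the same blood tubes as the general row. Children under 14 are handled by separate guidance. No row covers any other haematological cancer.

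The pairing rules refer to blood throughout:

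- Appendix 3, Tumour sample collection and processing, among the items essential for entry: "A germline blood sample should have been collected prior to resection or biopsy".
- Section 8.4.2: "DNA extracted from blood and tumour must be sent together to the Biorepository".
- Section 8.4.5: "Paired tumour and blood DNA samples extracted in accredited Genomic Medicine Centres".

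If not every sample can be taken, Appendix 3 says "the priority is to collect blood only for DNA extraction, followed by plasma, RNA (Paxgene) and then serum"; saliva is not ranked. The LIMS list asks for codes for DNA, RNA, serum and plasma and does not mention saliva. Table 4 in Section 8.4.2 has a block for DNA from saliva, but its amount is still open.

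On scope, Table 1 in Section 5.4 names the domain "CLL/leukaemia", and Section 3.3.2 allows further cancers to be nominated. The approved list is on the sponsor's website and is not part of the document.

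**The concern.** The text and the table give different instructions for the same patient. An adult with a blood cancer other than CLL is owed saliva under the text and none under the table.

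Section 3.3.2 has the pipelines call jointly across the tumour and germline pair to find somatic variants, and excludes patients without matched tumour and normal DNA. In a leukaemia, blood can carry the malignant clone. If blood is the only candidate normal, somatic variants appear in both files. They may then be removed as inherited, or reported as germline predisposition. Either outcome works against the cancer programme's first goal, the identification of novel driver mutations, and would not be obvious in the output.

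The gap extends to CLL. Saliva is collected there, but nothing tells the laboratory that saliva rather than blood is the normal.

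**Working it through.** **Rules side by side, adult with a non-CLL blood cancer**

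| Place in the protocol | Saliva taken? | Normal named |
|---|---|---|
| Appendix 3, Sample collection text | Yes | Not stated |
| Appendix 3, cancer volume table | No (dash) | Not stated |
| Appendix 3, Prioritisation of samples | Not ranked | Not stated |
| Appendix 3, tumour receipt | Not mentioned | Blood |
| Sections 8.4.2 (shipping) and 8.4.5 | Not mentioned | Blood paired with tumour |

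The first two rows contradict each other. No place names saliva as the normal.

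**Illustration of what a clone-bearing normal would do**

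Inputs from the protocol: 30X germline and 75X tumour (Section 3.4.1); a call needs at least three non-reference reads with one on each strand, and coverage is an over-dispersed gamma (Section 3.4.7). Assumptions: the gamma shape k and the clone fraction f in blood DNA, neither of which is given; a clonal heterozygous variant; reads falling on either strand with probability one half.

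With depth D and variant allele fraction v, the variant reads X are negative binomial with mean m = D × v and shape k. Then

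P(call) = Σ over x ≥ 3 of P(X = x) × (1 − 2 × 0.5^x).

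*Step 1: the protocol's own sensitivities.* Section 3.4.7 gives 99% for a 30X germline variant (v = 0.5), 99% for 75X at 50% cellularity (v = 0.25) and 96% for 75X at 30% cellularity (v = 0.15). The model gives:

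- k = 6: 98.2%, 99.2%, 95.6%
- k = 8: 98.9%, 99.6%, 96.7%
- k = 10: 99.2%, 99.7%, 97.3%

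All lie within 2 percentage points of the protocol, so k from 6 to 10 is a reasonable range.

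*Step 2: blood as the normal.* Here v = f/2 and m = 30 × f/2. Worked case, f = 0.2 and k = 6:

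- m = 3; P(0) = (6/9)^6 = 0.0878, P(1) = 0.1756, P(2) = 0.2049, so P(X ≥ 3) = 0.5318.
- Strand term: the sum of 0.5^x P(X = x) over all x is (6/7.5)^6 = 0.2621. Removing x = 0, 1, 2 leaves 0.2621 − 0.0878 − 0.0878 − 0.0512 = 0.0353.
- P(call) = 0.5318 − 2 × 0.0353 = 0.461.

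| Clone fraction f (assumed) | Expected variant reads | P(call), k = 6 | P(call), k = 10 |
|---|---|---|---|
| 0.05 | 0.75 | 0.039 | 0.036 |
| 0.10 | 1.5 | 0.166 | 0.161 |
| 0.20 | 3.0 | 0.461 | 0.472 |
| 0.30 | 4.5 | 0.672 | 0.697 |
| 0.50 | 7.5 | 0.874 | 0.902 |

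Plain Poisson coverage without the strand condition gives higher values (0.191, 0.577, 0.826 and 0.980 at 10%, 20%, 30% and 50%), but it departs from the protocol's own coverage model and calling rule.

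**The case against.** The strongest reply is that the saliva rule stands directly above the table and covers every haematological cancer, so a site that reads the whole section collects saliva. That is right, and it limits the point to a risk from conflicting instructions. A reader might infer that the protocol plans to sequence blood cancers against contaminated normals; it does not say so.

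Scope is also uncertain. The domain label comes from a list that the protocol calls representative of its pilots and open to change. If CLL were the only approved blood cancer, the missing rows would affect nobody yet. The unnamed normal in CLL would remain.

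The shipping sentence in Section 8.4.2 follows the FFPE table, and the tumour-receipt rule refers to resection and biopsy, so both sit in largely solid-tumour text. If they are read as not applying to leukaemia, however, no pairing rule for blood cancers is left.

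There are partial safeguards. The request form in Section 8.4.2 records whether each DNA is germline or tumour, but does not fix which source to use. Table 4 recognises saliva as a sequencing source. Section 3.3.2 requires the tumour to be analysed separately as well, because of tumour contamination in the germline sample. That step can recover lesions in known cancer genes, but without a clean normal it cannot tell a novel somatic variant from a rare inherited one.

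Finally, meeting the calling rule in the normal is not the same as removal by a joint caller, whose behaviour the protocol does not specify.

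**Conclusion.** The inconsistency is real and the table is wrong as written: it omits a sample that the text above it requires, and the matched normal for blood cancers is named nowhere. It should be fixed.

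The consequence is conditional. It needs an accepted non-CLL blood cancer and a site that works from the table, or a CLL case in which the laboratory pairs the tumour with blood. It also needs blood that carries the clone. Under the assumptions above, the chance that a clonal heterozygous variant is called in the blood normal is about 0.16 to 0.17 at a 10% clone, 0.46 to 0.47 at 20%, 0.67 to 0.70 at 30% and 0.87 to 0.90 at 50%. These figures show how quickly the normal loses its value. They do not estimate how many variants the project would lose.

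A reader might go further and conclude that blood should be the tumour sample in every haematological cancer, or that these patients must be excluded for want of a matched normal. The documents support neither: the tumour source is not stated by cancer type, and the text does ask for saliva, which could supply the normal.

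**What to change.** - In the Appendix 3 cancer table, change the CLL row label to cover all haematological cancers, so that it agrees with the text.
- In Sections 8.4.2 and 8.4.5 and in the tumour-receipt list of Appendix 3, add that for haematological cancers the matched normal is the non-blood (saliva) DNA and not blood. State the tumour source for each cancer type, since it is not blood in every one.
- Add saliva to the priority order and to the LIMS sample codes in Appendix 3, so that blood DNA and saliva DNA from one patient can be told apart.
- Complete the saliva DNA amount in Table 4 before such patients are sequenced.

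The cost is a row label, a few sentences and one 2 ml saliva kit for each non-CLL patient, which the text already asks for. The downside is that saliva DNA can be lower in yield and can itself contain leucocytes, so some samples will need a check for residual clone or a repeat.

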Appendix 4 Genomics England Governance and Committees

Appendix 5 | Genomics England Disease List Nomination Process

Please refer to **www.genomicsengland.co.uk** for further details.

Appendix 6 | Letter of Insurance

[name]

15th October 2014

[name], Chief Scientist, Genomics England Ltd [name]

Dear [name]

100,000 Genomes Project – disclosure of genome results for insurance purposes

I am writing in my capacity as the genomics policy lead in the Department of Health to clarify the current policy regarding the use of genetic and genomic information by insurance companies. I am aware that this is potentially a concern for participants in the 100,000 Genomes Project, especially given the novel nature of the project and the long-term storage, analysis and feedback that is envisioned for the project.

The use of genetic test information by insurers is the subject of an agreement between the Government and the Association of British Insurers (ABI). It is set out in the Concordat and Moratorium on Genetics and Insurance last updated and published in 2011. For the purposes of this project the key feature is that the insurers will not require the disclosure of:

"a predictive or diagnostic test result acquired as part of clinical research. To avoid doubt, customers may be asked to disclose details of any symptoms, diagnosis or treatment received outside of the clinical research programme, even if those relate to a condition they found out about through the research programme."

We have agreement from the ABI that the wording used in the Patient Information Sheet is in line with their interpretation of the current policy. The ABI are supportive of the aims of clinical research generally and of the 100,000 Genomes Project particularly. I am sure that they are willing to work with the Department and Genomics England to give specific guidance given the high profile nature of this project. The initial patient engagement suggests that further detailed Q&A for patients, clinicians and insurance companies may be necessary around the interpretation of the Concordat and Moratorium in relation to the feedback of secondary findings.

The key issues that the agreement covers are the uses of results from clinical genetic tests for highly penetrant late onset disorders. At present, the results of such tests do not need to be disclosed unless they are approved by an independent panel and are for policies over the financial threshold (£500,000 for life insurance). The only approved test is for Huntington's disease for Life Insurance. Even if the insurance companies were minded to make applications for the other conditions that may be returned as pertinent or incidental findings the timescale is likely to be many months which would give ample notice of a possible need for an amendment of the Patient Information Sheet.

Insurers do expect to be told about symptom, diagnoses or treatment if they request information at the application stage or via a medical report. They may ask for information about family history but many will be willing to consider favourable genetic test results even if they are not approved by the independent panel.

Turning to the longer term, the currently published Concordat and Moratorium states that the agreement will be reviewed in 2014 and will expire in 2017 if not renewed. I am pleased to advise you that we have reached agreement with the ABI that the Concordat and Moratorium will be extended until 2019 with a review in 2016. We are in the process of finalising the announcement and intend for this to be made public in the autumn and before recruitment begins via the NHS Genomic Medicine Centres.

Looking beyond 2019 is difficult as the 2016 review will need to be conducted in light of the priorities of the Government of the day. However, it has been a long-standing position in successive administrations that people should not be deterred from accessing healthcare or research opportunities because of concerns about insurance. In the most recent major review of discrimination legislation, in 2008 the Government decided not to not to extend protection against discrimination on the ground of genetic predisposition because "the existing arrangements for a voluntary moratorium on insurers' use of predictive genetic test results ... along with continued monitoring of the use of genetic testing in the UK should provide sufficient reassurance".

